## 9.5.3 Transvaginal Ultrasound

## 9.5.3.1 Ovarian Cysts

The presence of ovarian cysts will be noted at Baseline and each relevant post-baseline visit during the placebo-controlled and open-label Treatment Periods. The ovarian findings included complex ovarian cyst > 3.5 cm, simple ovarian cyst > 5 cm or endometriomas > 3 cm. For the Safety Analysis Set, the number and percentage of subjects with the pre-defined complex ovarian cysts and simple ovarian cysts will be summarized by treatment group at each relevant visit during the Treatment Period.

For each TAU/TVU assessment, information for ovarian findings from the cysts assessment may be available for more than one cyst at more than one ovary location (left and/or right). The subject with multiple cyst findings was counted once in the numerator and denominator when reporting the number and percentage of subjects in the relevant category of ovarian findings. A listing included all results across multiple cysts findings from multiple assessments (where available) from subjects who had ovarian findings.

## 9.5.3.2 Endometrial Thickness

For the Safety Analysis Set, the endometrial thickness at each relevant visit during the Treatment Period will be summarized with descriptive statistics. Additionally, analysis of change in endometrial thickness from Baseline to each relevant visit during the Treatment Period will be performed. The mean change from Baseline each relevant visit during the 12-month placebo-controlled Treatment Period will be compared between the elagolix treatment group and placebo using one-way ANOVA with treatment as the main effect; no comparison will be conducted during the open-label Treatment period.

In addition, the number and percentage of subjects with endometrial thickness of < 8 mm,  $\geq 8 \text{ mm}$  and  $\leq 12 \text{ mm}$ , > 12 mm and  $\leq 18 \text{ mm}$ , and > 18 mm will be summarized by treatment group at each relevant visit during the Treatment Period. Elagolix group will be compared to placebo using a Chi-squared test during the 12-month placebo-controlled

Treatment Period. No comparisons will be conducted during the open-label Treatment Period.

## 9.5.4 Endometrial Biopsy

For the Safety Analysis Set, the number and percentage of subjects in each category of endometrial biopsy results will be summarized by treatment group at each relevant visit during the placebo-controlled and open-label Treatment Periods. If multiple assessments existed in a specific time window, all assessments will be displayed.

## 9.5.5 Pregnancy Results

For the Safety Analysis Set, pregnancies and outcomes will be summarized by treatment group for the Treatment Period (placebo-controlled and open-label) and Follow-up Period. Subjects with conception date by sponsor more than 30 days after the last dose of study drug will be included in the summaries for the Follow-up Period.

Listings will be prepared of all pregnancy test results for any subject who ever had a positive pregnancy test at any time point during the study.

Positive pregnancy test results (serum, urine, and both) and a listing of all positive pregnancy test results will be provided.

Pregnancy outcome will be summarized by treatment group. Additionally, a listing of pregnancy information will be provided. Pregnancy outcome includes:

- Number of pregnancies
- Live births
  - Pre-term (extremely pre-term: <28 weeks; very pre-term: 28 -

    < 32 weeks; moderate to late preterm: 32 < 37 weeks)

  - $\circ$  Term (37 < 42 weeks)
  - Post-term ( $\geq$  42 weeks)
- Spontaneous abortion (< 6, 6 13, > 13 weeks gestation)
- Termination of pregnancy

- Ectopic pregnancy
- Still birth
- Congenital anomaly
- Lost to follow-up
- Subjects refused to provide information
- Other
- Ongoing (pregnancy ongoing at end of study)
- Maternal exposure to Elagolix/Study drug (0, > 0 4, > 4 6, > 6 12, > 12 23, > 23 weeks)
- Embryo/Fetal exposure to Elagolix/Study drug assessed by the sponsor (0, > 0 4, > 4 6, > 6 12, > 12 weeks)

Annualized pregnancy rate during treatment will be reported by treatment group. The annualized pregnancy rate will be calculated as

Annualized pregnancy rate = (number of pregnancies/days of exposure to treatment) × 365

In addition, listings of fetal/newborn, infant post-delivery assessments, and infant during 6-12 month follow-up assessment will be provided.

The above information will be summarized primarily based on data collected on the pregnancy case report form. Information not directly obtained from the case report form will use the following definitions.

## Gestation day

Gestation Day 0 was calculated by subtracting the gestational age provided according to the first trimester ultrasound date from the first trimester ultrasound date. If no gestational age was provided, it will be imputed by subtracting 14 days from the midpoint between the subject's last negative pregnancy test date and the date of the positive pregnancy test.

#### Gestational age

Gestational age at delivery was calculated from gestation Day 0 to the date of delivery. Gestational age at abortion was calculated from gestation Day 0 to the date of abortion.

#### **Conception date**

Conception date by sponsor was calculated from the gestational age provided from the first trimester ultrasound, by adding 14 days to gestation Day 0. If no gestational age was provided, the conception date by sponsor was imputed as the midpoint between the subject's last negative pregnancy test date and the date of the positive pregnancy test.

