#### Year 2, 3 4 (Open-Label) Treatment Period (Continued):

A urine pregnancy test will be performed at each visit throughout the Treatment Period. Home urine pregnancy test kits will be provided to subjects for use at home for the study visits when subjects are not required to come to the site. Subjects will self-administer the test and report the results to the site during the scheduled phone contact visits. A positive urine pregnancy test must be confirmed with a serum pregnancy test. If a serum pregnancy test result is positive at any time during the Treatment Period, study drug will be discontinued. Subjects will be counseled at each visit on appropriate and effective forms of dual non-hormonal contraceptives to promote pregnancy prevention.

Subjects will continue to provide blood samples for Clinical Safety Labs, during the on-site visits.

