## Embryo/fetal exposure

Embryo/fetal exposure to study drug by sponsor was calculated from the conception date by site/sponsor to the date of maternal last dose of study drug.

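### The fallback conception date in SAP 9.5.5 makes no allowance for the delay before a pregnancy test turns positive, so it is late on average by that delay

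*SAP*

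**What the plan says.** SAP 9.5.5 dates a pregnancy from the first-trimester ultrasound by default: conception is obtained "by adding 14 days to gestation Day 0". The fallback applies only when no gestational age was provided.

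- Conception date: "the conception date by sponsor was imputed as the midpoint between" the last negative and the positive test dates.
- Gestation Day 0: "it will be imputed by subtracting 14 days from the midpoint between" the same two test dates.
- Embryo/fetal exposure: "calculated from the conception date by site/sponsor to the date of maternal last dose of study drug". It is tabulated in weeks as 0, >0–4, >4–6, >6–12 and >12.
- Gestational age at abortion runs from Day 0 to the abortion. Spontaneous abortions are banded as <6, 6–13 and >13 weeks.
- Period assignment: a pregnancy with "conception date by sponsor more than 30 days after the last dose of study drug" is counted in the Follow-up Period.

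The two fallback rules agree with each other, since (midpoint − 14) + 14 is the midpoint. Neither has a detection-lag term, and no lag value appears in either document. The SAP also does not say which positive test counts, although the protocol requires a positive urine test to be confirmed by a serum test.

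**The concern.** The midpoint would be the natural estimate if a test became positive at the moment of conception. It becomes positive later. A negative test therefore does not show that conception had not yet occurred, and the interval that contains conception lies earlier than the interval between the tests. Using the unshifted midpoint dates conception too late on average. It makes losses look younger and drug exposure in early pregnancy look shorter, which is the less cautious direction for a safety summary.

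SAP Appendix A names spontaneous abortion and teratogenicity as items of safety interest. Protocol 3.2.3 reports two pregnancies with congenital malformations in earlier Phase 2 studies. It cites one on-treatment pregnancy in the Phase 2b fibroid study and four in Phase 3 studies. With counts that small, one misplaced case visibly changes a table.

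**Working it through.** The documents state no figure for this bias, so there is none to reproduce.

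**Inputs from the documents**
- Test schedule: "A urine pregnancy test will be performed at each visit throughout the Treatment Period" (Protocol synopsis). Visits are monthly and a month is 28 days (Protocol 1.3), so the on-schedule test interval is G = 28 days. If both visits use the full ±4-day on-site window (Protocol Table 1), G runs from 20 to 36.
- Last dose: drug is held after a positive urine test (Protocol 5.3.1.1, Pregnancy Testing), so the last dose is taken to fall at the positive test.

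**Assumptions**
- The lag L from conception to a positive test is 8 to 14 days; L = 0 is shown for reference.
- The moment of turning positive is uniform between the two tests.

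**Model.** Let N be the last negative and P the positive test, with P − N = G.
- Conception lies in (N − L, P − L], centred at (N + P)/2 − L.
- The SAP date is (N + P)/2, so mean lateness is L for any G.
- Individual error runs from L − G/2 to L + G/2.
- Share dated too late = (G/2 + L)/G, capped at 1.
- SAP exposure = P − (N + P)/2 = G/2 = 14 days.
- True exposure runs from L to L + G, with mean L + G/2. The share above 28 days is L/28.

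| L (days) | Mean lateness | Individual error | Dated too late | SAP exposure | True exposure (mean) | True exposure >28 days |
|---|---|---|---|---|---|---|
| 0 | 0 | −14 to +14 | 50% | 14 | 0–28 (14) | 0% |
| 8 | 8 | −6 to +22 | 79% | 14 | 8–36 (22) | 29% |
| 12 | 12 | −2 to +26 | 93% | 14 | 12–40 (26) | 43% |
| 14 | 14 | 0 to +28 | 100% | 14 | 14–42 (28) | 50% |

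**Gestational age.** At detection the SAP gives 14 + 14 = 28 days. Shifting by the lag gives 28 + L = 36 to 42 days. A loss t days after detection stays below 6 weeks (42 days) under the SAP rule for t < 14. With the lag it reaches 42 days once t ≥ 14 − L, that is t ≥ 6 (L = 8) or t ≥ 0 (L = 14). Losses between that point and day 14 move from <6 to 6–13 weeks.

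**Exposure band.** Subtracting the lag gives 14 + L = 22 to 28 days, for example 26 at L = 12. All of these remain in >0–4 weeks. The earliest feasible conception date, N − L, gives 28 + L = 36 to 42 days (>4–6 weeks). The latest, P − L, gives L = 8 to 14 days (>0–4 weeks).

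**Period assignment.** The lag changes the period only if the midpoint m satisfies 30 < m ≤ 30 + L days after the last dose, so at most days 30 to 44. Scheduled tests do not produce this:
- Negative at end of treatment, positive at Follow-up Month 1 (day 28 ± 7): m = 14, at most 35/2 = 17.5.
- Negative at Follow-up Month 1, positive at Month 6: m = (28 + 168)/2 = 98, or 84 to 90 after subtracting 8 to 14.

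**Effect of the choice of lag.** If true lags were uniform on 8 to 14 days (mean 11), mean lateness would be 11 days with no correction. It would be +3 after subtracting 8, 0 after subtracting 11, and −3 after subtracting 14.

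**The case against.** The strongest reply is that this is a last-resort rule with little reach. The protocol requires a first-trimester ultrasound for pregnancies up to 30 days after the last dose. SAP 9.5.5 relies mainly on the pregnancy case report form and uses these definitions only for what the form does not supply. The summaries are descriptive, all test results are listed for any subject who ever tested positive, and teratogenicity is followed by reviewing outcomes. All of that stands. It limits the importance of the point without removing the bias. It is tempting to add that the imputed cases will be mainly early losses and terminations; that is plausible, but neither document says so.

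A reader might infer three stronger things that the documents do not support.

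- *That every imputed date is 8 to 14 days late.* The lag is an outside assumption and the lateness is an average. At L = 8 with 28-day tests, 6/28 = 21% of cases are dated too early.
- *That the rule moves treatment-period pregnancies into follow-up at scheduled tests.* It does so only for unscheduled or missed tests with a midpoint roughly 30 to 44 days after the last dose.
- *That subtracting a lag repairs the exposure bands.* On-schedule cases stay in >0–4 weeks. Assigning the earliest feasible date instead would put all of them in >4–6 weeks, which at L = 12 is too high for 57%. The 28-day test interval limits what any single date can show.

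**Conclusion.** The point holds as a bias in a stated rule, with small scope. For any positive lag, fallback conception and Day 0 are late on average by that lag. Under an assumed lag of 8 to 14 days and 28-day testing, gestational age at detection is 28 days where 36 to 42 is expected, and some losses within two weeks of detection are banded <6 instead of 6–13 weeks. Embryo/fetal exposure is 14 days against a true mean of 22 to 28. The exposure figure further assumes dosing up to the positive test. If the last dose came before the imputed conception date, the formula gives a negative number, and the SAP does not say how that is handled. Counting a later confirmatory serum test as the positive test would move the midpoint later still. Only pregnancies without ultrasound dating are affected.

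**What to change.** In SAP 9.5.5, under Gestation day and Conception date:

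1. Set imputed conception to the midpoint minus a pre-specified detection lag, and Day 0 to that date minus 14 days.
2. State that the date of the first positive test is used.
3. Flag imputed cases in the tables and listings.
4. List the earliest and latest feasible conception dates (last negative minus lag, first positive minus lag) with the exposure and gestational-age bands that each implies. Present these as a sensitivity display and not as the assigned band.

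This takes a few sentences of SAP text and a small programming change, with no new data. A lag must be chosen in advance without support from these documents, so its source should be stated. The individual uncertainty of ±14 days at 28-day testing remains, which is why the feasible range should be shown.

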#### Maternal exposure

Maternal exposure to study drug was calculated as the last dose date of study drug – the first dose date of study drug + 1.

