#### **Definition of Terms**

Washout Period The minimum interval of time for washout of hormonal therapy

(if applicable) or other prohibited medications (if applicable).

Screening Period The approximately 2.5 to 5 month period prior to

randomization on Day 1, when screening procedures are performed to establish eligibility. Subjects may either enter the Screening Period directly, if no washout is required, or enter

after completing the Washout Period (if applicable).

Day 1 (Randomization) or Treatment

Period Day 1

The day a subject takes her first dose of study drug. Day 1 will occur between the first and tenth day of the onset (first day with

full menstrual flow) of menses.

Month A month is defined as 28 days.

Product Collection Visits (PCVs) Visits at which subjects return used sanitary products for

assessment of alkaline hematin levels (during screening); visits should occur within approximately 5 days after the last sanitary product was collected during a bleeding and/or spotting

product was collected during a bleeding and/or spotting

episode.

Heavy Menstrual Bleeding Menorrhagia or > 80 mL blood loss

2.0	Table of Contents	
1.0	Title Page	1
1.1	Protocol Amendment: Summary of Changes	2
1.2	Synopsis	
1.3	List of Abbreviations and Definition of Terms	
2.0	Table of Contents	14
3.0	Introduction	19
3.1	Uterine Fibroids	19
3.2	Elagolix	20
3.2.1	Preclinical Experience	20
3.2.1.1	Toxicology	20
3.2.2	Clinical Experience	20
3.2.3	Pregnancy in Elagolix Studies	27
3.3	Estradiol/Norethindrone Acetate	28
3.4	Differences Statement	28
3.5	Benefits and Risks	29
4.0	Study Objectives	30
5.0	Investigational Plan	30
5.1	Overall Study Design and Plan: Description	30
5.2	Selection of Study Population	40
5.2.1	Inclusion Criteria	41
5.2.2	Exclusion Criteria	43
5.2.3	Prior and Concomitant Therapy	48
5.2.3.1	Prior Hormonal/Anti-Hormonal Medications	49
5.2.3.2	Concomitant Therapy	51
5.2.3.3	Iron Supplementation	51
5.2.3.4	Concomitant Use of Corticosteroids	52
5.2.3.5	Prohibited Therapy	52
5.2.4	Contraception Recommendations	56
5.3	Efficacy, Pharmacokinetic, Biomarker, Optional Exploratory Research Samples and Safety Assessments/Variables	50
5.3.1	Efficacy and Safety Measurements Assessed and Flow Chart	
J.J.1	Littledey and butery wiedsarements Assessed and I low Chart	

5.3.1.1	Study Procedures	60
5.3.1.2	Collection and Handling of Biomarker and Optional Explorator	y
	Research Samples	89
5.3.2	Drug Concentration Measurements	90

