## Year 1 Treatment Period

The elagolix study drug, consisting of elagolix or matching placebo, will be supplied in a carton. The E2/NETA study drug, consisting of E2/NETA or matching placebo, will be supplied in a separate carton. The subject will take the first elagolix dose (morning dose) and first E2/NETA dose of study drug at the study site on Day 1 (Randomization) whether the subjects visit is scheduled in the morning or afternoon. Subjects will be instructed to self-administer their study drug throughout the 12-month Treatment Period.

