## 2.2 Study Design Overview

This Phase 3b, randomized, 12-month double-blind placebo-controlled, 36 month openlabel, multi-center study is designed to evaluate the safety of elagolix with add-back therapy in women with HMB associated with uterine fibroids.

Approximately 500 subjects will be randomized in a 2:1 ratio to one of the following 2 treatment groups:

- Elagolix 300 mg BID plus E2/NETA (estradiol 1.0 mg/norethindrone acetate 0.5 mg QD) (n = 333) for 48 months
- 2. Placebo (n = 167) for 12 months

Subjects randomized to elagolix 300 mg BID plus E2/NETA in the 12-month Treatment Period will receive the same treatment during the open-label Treatment Period. Subject randomized to placebo in the 12-month Treatment Period will switch to elagolix 300 mg BID plus E2/NETA during the open-label Treatment Period after completing the 12-month Treatment Period.

The total duration for a subject's participation in this study is approximately 77 months, consisting of the following 4 study periods:

- 1. Washout Period up to 10 months prior to Screening (only applicable if subject is taking exclusionary medication at the time of consent; duration of washout depends on the type of exclusionary medication being taken).
- 2. Screening Period approximately 2.5 to 5 months prior to first dose of study drug.
- 3. Treatment Period up to 48-month treatment duration
- 4. Post-Treatment Follow-Up Period up to 12 months duration following the last dose of study drug. Subjects are expected to enter Post-Treatment Follow-Up after completing Treatment Period Month 48, or at any time a subject prematurely discontinues during the Treatment Period.

The Study Schematic is shown below in Figure 1.

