#### All Elagolix plus E2/NETA Analysis Set:

For subjects who received at least 1 dose of elagolix plus E2/NETA (either in the placebocontrolled or open-label Treatment Period), the duration of treatment is defined as the last dose date of receiving elagolix plus E2/NETA minus the first dose date of receiving elagolix plus E2/NETA plus 1 day.

In addition, the number and percentage of subjects in each treatment duration interval  $(1 - < 84 \text{ days}, 84 - < 168 \text{ days}, 168 - < 252 \text{ days}, 252 - < 336 \text{ days}, 336 - < 420 \text{ days}, 420 - < 504 \text{ days}, 504 - < 588 \text{ days}, 588 - < 672 \text{ days}, 672 - < 756 \text{ days}, 756 - < 840 \text{ days}, 840 - < 924 \text{ days}, 924 - < 1008 \text{ days}, 1008 - < 1092 \text{ days}, 1092 - < 1176 \text{ days}, 1176 - < 1260 \text{ days}, 1260 - < 1344 \text{ days}, \ge 1344 \text{ days})$  will be summarized.

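### Maternal exposure in the pregnancy table runs from the first dose of study drug, so women who switched from placebo carry about 48 weeks of placebo into a row headed as elagolix exposure

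*SAP*

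**What the plan says.** - SAP 9.5.5, under Maternal exposure, gives the formula: "Maternal exposure to study drug was calculated as the last dose date of study drug", minus "the first dose date of study drug + 1". It restricts neither the drug nor the study period.
- The list of pregnancy outputs in SAP 9.5.5 has a row headed "Maternal exposure to Elagolix/Study drug", with bands of 0, >0–4, >4–6, >6–12, >12–23 and >23 weeks.
- The population includes the placebo arm: "For the Safety Analysis Set, pregnancies and outcomes will be summarized by treatment group".
- The Protocol's Definition of Terms describes Day 1 as "The day a subject takes her first dose of study drug", for both arms. Protocol 5.5.1 (Year 1 Treatment Period) makes clear that study drug covers placebo: "consisting of elagolix or matching placebo, will be supplied in a carton".
- SAP 2.2 describes the switch: "Subject randomized to placebo in the 12-month Treatment Period will switch to elagolix 300 mg". It takes place after the 12-month period is complete.
- For the All Elagolix plus E2/NETA Analysis Set, SAP 6.0 uses a different clock. Duration is the last date of elagolix plus E2/NETA "minus the first dose date of receiving elagolix plus E2/NETA plus 1 day". The adverse-event rates in SAP 9.2.4 also start at the first elagolix plus E2/NETA dose.

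**The concern.** A woman who starts on placebo and switches has two start dates: the first study drug (placebo, Day 1) and the first elagolix (about Month 12). The maternal exposure formula uses the first of these, although the row heading puts elagolix first. Her placebo year is therefore reported as if it were time on the drug of interest. The top band begins at 23 weeks, less than half the length of the placebo period, so the bands cannot show whether she had been on elagolix for one week or for two years.

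Pregnancy is a listed safety endpoint (SAP 3.4), and earlier programs saw few on-treatment pregnancies: Protocol 3.2.3 reports one in the Phase 2b fibroid study and four in the Phase 3 studies. In a table of that size, one misplaced case is visible.

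**Working it through.** **Inputs.** A study month is 28 days (Protocol, Definition of Terms). Placebo lasts 12 months and the open-label period 36 months (SAP 2.2). On-site visits have a window of ±4 days (Protocol Table 1). The top band starts above 23 weeks (SAP 9.5.5).

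**Reproducing the SAP's own figures.** 12 × 28 = 336, 36 × 28 = 1008 and 48 × 28 = 1344 days. These are the lower limits of the top duration intervals in SAP 6.0 for the placebo-controlled period, the open-label period and the All Elagolix set, so the 28-day month is the right unit.

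**Exposure of a switcher under the present rule.** Last minus first study-drug date, plus 1, equals placebo days plus elagolix days, provided that there is no gap between the two; a gap would lengthen it. With 336 placebo days:

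| Days on elagolix | Elagolix only: weeks | Band | Present rule: days | Weeks | Band |
|---|---|---|---|---|---|
| 1 | 0.1 | >0–4 | 337 | 48.1 | >23 |
| 28 | 4.0 | >0–4 | 364 | 52.0 | >23 |
| 42 | 6.0 | >4–6 | 378 | 54.0 | >23 |
| 84 | 12.0 | >6–12 | 420 | 60.0 | >23 |
| 161 | 23.0 | >12–23 | 497 | 71.0 | >23 |
| 162 | 23.1 | >23 | 498 | 71.1 | >23 |
| 1008 | 144.0 | >23 | 1344 | 192.0 | >23 |

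The overstatement is 336 / 7 = 48 weeks in every line. The visit window moves the switch to between day 332 and day 340. Even at the earliest, one elagolix day gives 333 / 7 = 47.6 weeks, about twice the 23-week limit.

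**When the band is wrong.** Elagolix-only exposure passes 23 weeks after 23 × 7 = 161 days. The band is therefore wrong for 161 elagolix days or fewer, which is 161 / 1008 = 16% of the open-label period. Beyond that, the duration is still 48 weeks too long, but the band is correct.

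**Women who took only placebo.** The formula gives at least 1 day to anyone dosed, so a placebo-year pregnancy falls in a positive band, and in >23 weeks once dosing has lasted 162 days.

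**The zero band.** Everyone in the Safety Analysis Set took at least one dose (SAP 4.0), so the smallest possible value is 1 day and the zero band stays empty. That band makes sense only if women without elagolix were meant to score 0.

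**The case against.** **The label can be read as total study-drug time.** It says elagolix or study drug, and the formula says study drug. On that reading the two agree. But the row then reports no elagolix exposure and its zero band has no use, so the text needs a change on either reading.

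**The comparison with SAP 6.0 and 9.2.4 crosses populations.** Those rules serve the All Elagolix set, whereas the pregnancy outputs use the Safety Analysis Set, for which SAP 6.0 defines duration by period. This stands: the sections do not contradict each other directly. They do show that the SAP already has an elagolix-only definition. Reading the maternal rule by period would help switchers, but the rule does not say so, and it would drop the first year for women randomized to elagolix.

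**Treatment group and period may separate the cases.** Placebo-year pregnancies sit in the placebo column. So do switchers, because SAP 4.0 groups women by the treatment received in Year 1. SAP 9.1 provides safety summaries by period, which may keep the two kinds apart, but SAP 9.5.5 is not explicit. Separate tables would not correct a switcher's value.

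**The fetal measure and the listing.** A reader might infer that the analysis of teratogenicity or miscarriage is distorted. The documents do not support this. Embryo/fetal exposure has its own row and starts at conception, so it holds no placebo time for a woman who conceives after the switch; a conception before the switch is the exception. SAP 9.5.5 does not tabulate outcome by maternal exposure. SAP Appendix A finds spontaneous abortion by a MedDRA query and teratogenicity by review of outcomes, and neither uses the maternal band. A listing of pregnancy information also allows each case to be read on its own. All of this stands and limits the consequence.

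**Conclusion.** The defect is real and confined to one descriptive row. As written, every switcher with an open-label pregnancy has her elagolix exposure overstated by about 48 weeks (47.4 to 48.6 with the visit window) and is placed in >23 weeks. The band itself is wrong only for elagolix exposure of 161 days or fewer. Placebo-only pregnancies receive positive exposure, and the zero band cannot be used. This rests on taking study drug to include placebo, as the Protocol does, and on reading the row as elagolix exposure, which the zero band favors.

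Two stronger readings should be avoided. One is that every switcher's pregnancy is in the wrong band; after 161 days on elagolix the band is right. The other is to treat 16% as the share of pregnancies affected. It is a share of time. The share of pregnancies depends on dropout, on when conceptions occur, and on the last dose, which normally comes after conception, so fewer conceptions are affected than the time share suggests. The documents give no dropout curve and no expected number of pregnancies. With required dual contraception and the few pregnancies seen earlier, the count is likely small.

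**What to change.** In the Maternal exposure definition of SAP 9.5.5, replace the study-drug dates with elagolix dates: last minus first dose date of elagolix plus E2/NETA, plus 1, as in SAP 6.0 for the All Elagolix set. Assign 0 to women who received only placebo. Label the row as maternal exposure to elagolix.

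This costs one definition and one label. It needs no new data, since SAP 6.0 and 9.2.4 already use the same dates; any pregnancy table already run under the present rule would need that row rerun. A separate row for placebo exposure, or tabulation by treatment at conception, would be an optional addition and is not needed to correct the defect.
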